## **9.7 Quality Assurance for General Laboratory Testing**

Local laboratories will perform hematology, chemistry, liver function, lipids, hepatitis, STI, CD4, RNA and urinalysis testing as indicated in each relevant SOE.

## **9.8 Quality Assurance for CD4 Cell Count Testing**

Local laboratories may also perform CD4 cell count testing as indicated in [Appendix II](#).

## **9.9 Quality Assurance for HIV RNA Testing**

Local laboratories may also perform HIV RNA/viral load testing (platform and test kit approved by the HPTN LC) as indicated in [Appendix II](#) or for evaluation of possible acute HIV infection.

## **9.10 Specimen Storage and Possible Future Research Testing**

Study sites will store specimens collected in this study at least through the end of the study (completion of all study-related testing, including testing at the HPTN LC, which is typically one year post main paper publication). In addition, study participants will be asked to provide written informed consent for the collected samples to be stored after the end of the study, for possible future non-protocol listed testing. The specimens of participants who do not consent to long-term storage and additional testing will be collected and remain stored as planned, and then be destroyed after all of the protocol specified testing (including assessments at the HPTN LC) has been completed and approval from the protocol team and network leadership is provided.

Samples from participants who did not successfully enroll in the study may be discarded once sample lists are provided by the HPTN LC in consultation with the HPTN SDMC.

### **9.11 Biohazard Containment**

As the transmission of HIV and other blood-borne pathogens can occur through contact with contaminated needles, blood, and blood products, appropriate blood and secretion precautions will be employed by all personnel in the drawing of blood and shipping and handling of all specimens for this study, as currently recommended by the US CDC. All infectious specimens will be transported in accordance with United States regulations (42 CFR 72) and in accordance with IATA.

## **10.0 ADMINISTRATIVE PROCEDURES**

### **10.1 Protocol Registration**

Initial Registration of the protocol by the DAIDS PRO is required prior to implementation of this protocol. As part of this process, each site must have the protocol and protocol informed consent form(s) (ICFs) approved, as appropriate, by their IRB/EC and any other applicable regulatory entity (RE). Upon receiving final approval, sites will submit all required protocol registration documents to the DAIDS PRO at the DAIDS RSC. The DAIDS PRO will review the submitted protocol registration packet to ensure that all of the required documents have been received. In the case of Initial Registration, site-specific ICFs *WILL* be reviewed and approved by the DAIDS PRO. Sites will receive an Initial Registration Notification from the DAIDS PRO that indicates successful completion of the protocol registration process. A copy of the Initial Registration Notification should be retained in the site's regulatory files.

Following Initial Registration, any full protocol amendments require submission of a protocol registration packet to the DAIDS PRO as described above; however, the DAIDS PRO *WILL NOT* review and approve site-specific ICFs. Upon receiving final IRB/EC and any other applicable RE approval(s) for an amendment, sites should implement the amendment immediately. Sites will receive a Registration Notification when the DAIDS PRO receives a complete registration packet. A copy of the Amendment Registration Notification should be retained in the site's regulatory files.

There may be cases where a site submits as their Initial Registration a protocol amendment (Version 2.0 or higher of a protocol); in such cases, the instructions for Initial Registration will be followed.

For additional information on the protocol registration process and specific documents required for initial and amendment registrations, refer to the current version of the DAIDS Protocol Registration Manual, which can be found at <https://rsc.niaid.nih.gov/clinical-research-sites/daids-protocol-registration-policy-and-procedures-manual>.

### **10.2 Study Activation**

Pending successful protocol registration and submission of all required documents, the HPTN LOC staff will “activate” a site. Study implementation may not be initiated until a study activation notice is provided to the site by the HPTN LOC. In addition, if study “activation” is determined to be necessary for any subsequent amendments, study implementation may not be initiated until a study activation notice is provided to the site by the HPTN LOC.

### **10.3 Study Coordination**

DAIDS holds the Investigational New Drug (IND) application for this study. Copies of all regulatory documents submitted to this IND by DAIDS will be forwarded to ViiV Healthcare for cross-referencing with the company's other INDs for the study product(s). Assignment of all sponsor responsibilities for this study will be specified in a Clinical Trials Agreement executed between DAIDS and ViiV Healthcare.

Study implementation will be directed by this protocol as well as the SSP Manual. The SSP Manual, which will include links to the DAIDS SOPs for Source Documentation and Essential Documents, as well as links to the Manual for Expedited Reporting of AEs to DAIDS and the DAIDS Toxicity Tables, will outline procedures for conducting study visits; data and forms processing; AE assessment, management and reporting; dispensing study products and documenting product accountability; and other study operations.

Study CRFs will be developed by the study team and HPTN SDMC. Data will be transferred to the HPTN SDMC, entered, and cleaned using the MediData Rave electronic data management system. Queries routinely will be generated and distributed to the study sites for verification and resolution.

Close coordination between protocol team members will be necessary to track study progress, respond to queries about proper study implementation, and address other issues in a timely manner. Rates of accrual, adherence, follow-up, and AE incidence will be monitored closely by the team as well as the HPTN SMC. The protocol team's CMC will address issues related to study eligibility and AE management and reporting as needed to assure consistent case management, documentation, and information-sharing across sites.

### **10.4 Study Monitoring**

On-site study monitoring will be performed in accordance with DAIDS policies. Study monitors will visit the site to:

- verify compliance with human subjects and other research regulations and guidelines;
- assess adherence to the study protocol, study-specific procedures manual, and local counseling practices; and
- confirm the quality and accuracy of information collected at the study site and entered into the study database.

Site investigators will allow study monitors to inspect study facilities and documentation (e.g., informed consent forms, clinic and laboratory records, other source documents, CRFs), as well as observe the performance of study procedures. Investigators also will allow inspection of all study-related documentation by authorized representatives of the HPTN LOC, HPTN SDMC, HPTN LC, NIAID and/or its contractors; NICHD and/or its contractors (including Westat); site IRBs/ECs; other local, US, or international regulatory authorities (including the OHRP and US FDA); or, if appropriate, the HPTN's sIRB, Advarra, or ViiV. A site visit log will be maintained at each study site to document all visits.

Monitoring visits may be conducted on-site or remotely. Remote visits may include remote source document verification using methods specified for this purpose by NIAID. Remote monitoring visits may be performed in place of, or in addition to onsite visits to ensure the safety of study participants and data integrity. The site will make available study documents for site monitors to review utilizing a secure platform that is HIPAA and 21 CFR Part 11 compliant. Potential platform options include: Veeva SiteVault, site-controlled SharePoint or cloud-based portal, direct access to Electronic Medical Record (EMR), and Medidata Rave Imaging Solution. Other secure platforms that are 21 CFR Part 11 compliant may be utilized, as allowed by the DAIDS Office of Clinical Site Oversight (OCSO).

## **10.5 Protocol Compliance**

The study will be conducted in full compliance with the protocol. The protocol will not be amended without prior written approval by the Protocol Chair and DAIDS Medical Officer. All protocol amendments must be submitted to and approved by the relevant IRB(s) and the DAIDS RSC prior to implementing the amendment.

## **10.6 Investigator's Records**

The IoR will maintain, and store in a secure manner, complete, accurate, and current study records throughout the study. In accordance with Federal regulations, for each of the investigational products tested, the IoR will retain all study records for at least two years following the date of marketing approval for the study product for the indication in which it was studied, or if other applicable laws, regulations, policies, or other requirements (e.g., State, country-specific, and local laws, and sponsor or institutional policies) exist, the most stringent retention period will be followed. European Medicines Authority (EMA) requirements, which will apply to the parent protocol (HPTN 083), were the most demanding identified by DAIDS at the study-wide level. Based upon EMA requirements, sites should therefore plan to retain files (and any other study documentation) for more than 15 years from the end of data collection, or longer if required by local regulations.

If no marketing application is filed, or if the application is not approved, the records must be retained for two years after the US FDA is notified that the IND is discontinued, or if other applicable laws, regulations, policies, or other requirements (e.g., State, country-specific, and local laws, and sponsor or institutional policies) exist, the most stringent retention period will be followed.

Study records include administrative documentation — including protocol registration documents and all reports and correspondence relating to the study, as well as documentation related to each participant screened and/or enrolled in the study. This includes informed consent forms, locator forms, CRFs, notations of all contacts with the participant, and all other source documents.

Completion of a clinical research study occurs when the following activities have been completed:

- All research-related interventions or interactions with human subjects (e.g. when all subjects are off study);
- All protocol-required data collection of identifiable private information described in the IRB/EC-approved research plan;
- All analysis of identifiable private information described in the IRB/EC-approved research plan;

- Primary analysis of either identifiable private or de-identified information.

## **10.7        Use of Information and Publications**

Publication of the results of this study will be governed by HPTN policies. Any presentation, abstract, or manuscript will be submitted by the Investigator to the HPTN Manuscript Review Committee (MRC), DAIDS, and ViiV Healthcare for review prior to submission.

## **12.0 APPENDICES I – XVI**

## 12.1 APPENDIX I. SCHEDULE OF EVALUATIONS – ORAL PHASE (STEP 1)

WEEKS in Study (Shaded column = dispense oral product)	Screening	WEEK 0 Enrollment	WEEK 2	WEEK 4
ADMINISTRATIVE, BEHAVIORAL, REGULATORY				
Informed consent	X			
Locator information	X	X	X	X
Demographic information 	X	X		
HIV prevention counseling	X	X	X	X
Offer condoms	X	X	X	X
Patient Health Questionnaire-9 (PHQ-9)		X		
Behavioral/Acceptability Assessment (CASI)		X		X
CLINICAL EVALUATIONS & PROCEDURES				
Dispense study product (enough for 5 weeks)		X		
Observe participant take oral study product 		X	X	X
Adherence counseling/pill count (pill count Weeks 2 and 4 only)		X	X	X
Medical history, con meds, targeted physical exam 	X	X	X	X
Hep B vaccination (if needed) 			X	
Blood collection	X	X	X	X
Urine collection	X	X		
Rectal swab collection	X			
LOCAL LABORATORY EVALUATIONS & PROCEDURES				
HIV testing 	X	X	X	X
HBV and HCV testing 	X	X		
CBC with differential	X	X	X	X
Chemistry testing 	X	X	X	X
Liver function tests 	X	X		X
Fasting lipid profile 		X		
Syphilis testing	X			
GC/CT testing (urine, rectal, and oral pharyngeal swabs)	X			
Urinalysis (protein and glucose; this test can be done at either the clinic or in the local laboratory)		X		
Plasma storage 	X	X	X	X

### FOOTNOTES FOR APPENDIX I:

 Demographics may be collected and reported at either Screening or Enrollment.

 Staff are required to observe participants take one pill at Enrollment. If participants return with their pills at Weeks 2 & 4, staff will observe participant take one pill then as well, unless the participant has already taken oral study product that day. Participants must not be asked to take a second dose of oral study product for the sake of observation.

 Full physical exam is to be conducted during Enrollment. A targeted physical exam will be done at all other visits. Participant pulse, blood pressure and weight must be recorded at every visit. BMI must be calculated.

 The initial dose of the Hep B vaccination will ideally be given at Week 2, though there is flexibility around the timing of the vaccination. Subsequent doses may be given at different visits than indicated in this SOE, as long as sites follow manufacturer guideline timing.

 The HIV testing algorithm is provided in the SSP Manual. Testing for acute HIV must be negative and must be performed within the 14 days prior to enrollment of the participant. If HIV rapid testing is indicated, this testing may be performed in the clinic or the laboratory. At least one HIV assay result must be available and reviewed the same day as sample collection and before product is administered.

 Participants will be tested for Hepatitis B surface antibody (HBsAb), and Hepatitis B core antibody (HBcAb, total) at Screening or Enrollment. HbsAg and HCV Ab must be resulted and reviewed prior to enrollment.

 At Screening: Creatinine. At and after enrollment: BUN/urea, creatinine, CPK, calcium, phosphorous, glucose, amylase, and lipase.

 At Screening: ALT and TBili. At and after Enrollment: AST, ALT, total bilirubin, and alkaline phosphatase.

 Total cholesterol, HDL, triglycerides, and LDL (either calculated or measured). Participants must have fasted for at least 8 hours, preferably 12 hours, prior to sample collection. Do not collect or test if <8 hours fasting.

 Stored plasma will be used for Quality Assurance testing and other assessments at the HPTN LC ([see Section 9](#)). Assessments will be performed retrospectively; results will not be returned to study sites or participants, except as noted in SSP. Samples cannot be used by site or other lab for local purposes without specific instructions from the LC w/ CMC consult.

## 12.2 APPENDIX II. SCHEDULE OF EVALUATIONS – INJECTION PHASE (STEP 2)

WEEKS in Study (shaded column = injection visit)	Wk 5	Wk 6	Wk 9	Wk 10	Wk 17	Wk 18	Wk 25	Wk 26	Wk 33	Wk 34
ADMINISTRATIVE, BEHAVIORAL, REGULATORY										
Locator information	X	X	X	X	X	X	X	X	X	X
HIV prevention counseling	X	X	X	X	X	X	X	X	X	X
Condoms per local SOC	X	X	X	X	X	X	X	X	X	X
Behavioral/Acceptability assessment (CASI)	X		X		X		X		X	
Qualitative interviews begin (approximately)										X
CLINICAL EVALUATIONS & PROCEDURES										
Adherence, risk reduction counseling	X	X	X	X	X	X	X	X	X	X
Medical history  , concomitant medications, targeted physical exam	X	X	X	X	X	X	X	X	X	X
Hep B vaccination (if needed) 		X								X
Blood collection	X	X	X	X	X	X	X	X	X	X
Urine collection	X	X	X	X	X	X	X	X	X	X
Rectal swab collection					X					X
Injections for all participants	X		X		X		X		X	
ISR evaluation		X		X		X		X		X
Step 3 product choice discussion									X	X
Interviewer administered product choice assessment										X
If product chosen is oral PrEP: Provision of Tenofovir/Emtricitabine (Trade name: TDF/FTC, Truvada®) (3 months' worth)										X
LOCAL LABORATORY EVALUATIONS & PROCEDURES										
HIV testing 	X	X	X	X	X	X	X	X	X	X
CBC with differential	X	X	X	X	X	X	X	X	X	X
Chemistry testing 	X	X	X	X	X	X	X	X	X	X
Liver function testing 	X	X	X	X	X	X	X	X	X	X
Fasting lipid profile 										X
Syphilis testing										X
GC/CT testing (urine, rectal, and oral pharyngeal swabs)					X				X	
Urinalysis (protein, glucose; at the clinic or local lab)	X	X	X	X	X	X	X	X	X	X
Plasma storage 	X	X	X	X	X	X	X	X	X	X

## FOOTNOTES FOR APPENDIX II:

-  Medical history must include pulse, blood pressure, weight and Body Mass Index (BMI) calculated at each visit
-  The initial dose of the HBV vaccination is ideally given at Week 2, though there is flexibility around the timing of the vaccination. Subsequent doses may be given at different visits than indicated in this SOE, as long as sites follow manufacturer guideline timing.
-  The HIV testing algorithm is provided in the SSP Manual. If HIV rapid testing is indicated, this testing may be performed in the clinic or the laboratory. At least one HIV assay result must be available and reviewed the same day as sample collection and before product is administered.
-  BUN/urea, creatinine, CPK, calcium, phosphorous, glucose, amylase, and lipase.
-  AST, ALT, TBili, and alkaline phosphatase.
-  Total cholesterol, HDL, triglycerides, and LDL (either calculated or measured). Participants must have fasted for at least 8 hours, preferably 12 hours, prior to sample collection. Do not collect or test if <8 hours fasting. For participants who switch to Step 3 early (without having completed all 5 injections), the fasting lipid profile will be taken at the first visit after they transition off injections.
-  Stored plasma will be used for Quality Assurance testing and other assessments at the HPTN LC ([see Section 9](#)), including potential assay for plasma CAB concentrations.. Assessments will be performed retrospectively; results will not be returned to study sites or participants, except as noted in the SSP Manual. Samples cannot be used by site or other lab for local purposes without specific instructions from the LC w/ CMC consult.

## 12.3 APPENDIX III. SCHEDULE OF EVALUATIONS –FOLLOW-UP PHASE (STEP 3-ORAL PrEP)

WEEKS SINCE LAST INJECTION	Wk +8	Wk +12	Wk +24	Wk +36	Wk +48	Early Discontinuation
ADMINISTRATIVE, BEHAVIORAL, REGULATORY						
Locator information	X	X	X	X	X	X
HIV prevention & risk reduction counseling	X	X	X	X	X	X
Condoms per local SOC	X	X	X	X	X	X
Behavioral/Acceptability assessment (CASI)		X	X	X	X	X
CLINICAL EVALUATIONS & PROCEDURES						
Qualitative interviews continue (approximately)		X	X			
Medical history  , concomitant medications, targeted physical exam		X	X	X	X	
Hep B vaccination (if needed) 						X
Blood collection	X	X	X	X	X	
Urine collection			X		X	X
Rectal swab collection			X		X	
Provision of Tenofovir/Emtricitabine (Trade name: TDF/FTC, Truvada®) (3 months' worth)		X	X	X		X
LOCAL LABORATORY EVALUATIONS & PROCEDURES						
HIV testing 		X	X	X	X	
CBC with differential			X		X	X
Chemistry testing 		X	X	X	X	X
Liver function testing 		X	X	X	X	X
Syphilis testing			X			X
GC/CT testing (urine, rectal, and oral pharyngeal swabs)			X		X	
Urinalysis (protein, glucose; at the clinic or local lab)			X		X	X
Plasma storage 	X	X	X	X	X	
DBS storage		X	X		X	
HBsAb and HBcAb 					X	X
HCVAb					X	X

### FOOTNOTES FOR APPENDIX III:

 Medical history must include pulse, blood pressure, weight and Body Mass Index (BMI) calculated at each visit

 The initial dose of the HBV vaccination is ideally given at Week 2, though there is flexibility around the timing of the vaccination. Subsequent doses may be given at different visits than indicated in this SOE, as long as sites follow manufacturer guideline timing.

 The HIV testing algorithm is provided in the SSP Manual. If HIV rapid testing is indicated, this testing may be performed in the clinic or the laboratory. At least one HIV assay result must be available and reviewed the same day as sample collection and before product is administered.

 Creatinine only (for Step 3-Oral PrEP)..

 AST, ALT, TBili, and alkaline phosphatase.

 Stored plasma will be used for Quality Assurance testing and other assessments at the HPTN LC ([see Section 9](#)) including potential assay for plasma CAB concentrations. Assessments will be performed retrospectively; results will not be returned to study sites or participants, except as noted in SSP. Samples cannot be used by site or other lab for local purposes without specific instructions from the LC w/ CMC consult.

 HBsAb and HBcAb will be tested in participants who received the HBV vaccine.

**12.4 APPENDIX IV. SCHEDULE OF EVALUATIONS – FOLLOW-UP PHASE (STEP 3-INJECTION)**

WEEKS SINCE LAST INJECTION	Wk +8	Wk +16	Wk +24	Wk +32	Wk +40	Wk +48	Early Discontinuation
ADMINISTRATIVE, BEHAVIORAL, REGULATORY							
Locator information	X	X	X	X	X	X	X
HIV prevention & risk reduction counseling	X	X	X	X	X	X	X
Condoms per local SOC	X	X	X	X	X	X	X
Behavioral/Acceptability assessment (CASI)		X	X	X	X	X	X
CLINICAL EVALUATIONS & PROCEDURES							
Qualitative interviews continue (approximately)		X	X				
Medical history  , concomitant medications, targeted physical exam		X	X	X	X	X	
Hep B vaccination (if needed) 							X
Blood collection	X	X	X	X	X	X	
Urine collection			X			X	X
Rectal swab collection			X			X	
Injections (CAB LA)	X	X	X	X	X	X	X
ISR evaluation	X	X	X	X	X	X	X
Adherence counselling	X	X	X	X	X	X	X
LOCAL LABORATORY EVALUATIONS & PROCEDURES							
HIV testing 	X	X	X	X	X	X	X
CBC with differential			X			X	
Chemistry testing 	X		X			X	X
Liver function testing 	X		X			X	X
Syphilis testing			X				X
GC/CT testing (urine, rectal, and oral pharyngeal swabs)			X			X	X
Plasma storage 	X	X	X	X	X	X	
DBS storage		X	X		X	X	
HBsAb and HBcAb 						X	X
HCVAb						X	X

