### Step 3 – Follow-up Phase

Participants with confirmed HIV infection during Step 3 will not receive oral Tenofovir/Emtricitabine (Trade name: TDF/FTC, Truvada®) or CAB LA and will be followed per the SOE in [Appendix V](#) quarterly through study exit (following an initial +8 Week Visit). In addition, sites will have a standard operating procedure (SOP) that outlines a plan to facilitate immediate initiation of non-study ART and link with appropriate HIV services in the event that a participant becomes HIV-infected during any Step of the study, and in particular during Step 2 of the study, to prevent emergence of drug resistance. Participants who seroconvert will be referred for care; sites will not be responsible for the actual provision/payment of ART. Neither ART nor funds for provision of ART will be provided by the study.

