## **5.16 Criteria for Early Termination of Study Participation**

Participants may voluntarily withdraw from the study for any reason at any time (or their parents/guardians may, if they are under the legal age of consent). In general, for participants who withdraw consent from the study prematurely during a study visit, the requirements for that visit should be completed to the extent possible except for provision of study product and will be considered their final visit. When possible, a plan should be made to provide final laboratory results to the participant. For participants who inform the site in between visits that they wish to withdraw consent from the study, sites should make every effort to have the participant return any unused study product. Study staff will record the reason(s) for all withdrawals in participants' study records and consult procedures for early discontinuation.

Site IoRs may, with the agreement of the CMC, Protocol Chairs, DAIDS MO, and study statistician, withdraw participants before their scheduled termination visit to protect their safety, the safety of the staff, and/or if participants are unable or unwilling to comply with study procedures. Participants also may be withdrawn if the study sponsors, government or regulatory authorities (including the OHRP and US FDA), or site IRBs/ECs or ViiV terminate the study prior to its planned end date.

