2.1 General Design Considerations

HPTN083-01 is a phase IIB single arm trial designed to establish the minimum safety, tolerability and acceptability data needed to support the use of cabotegravir long-acting injection (CAB LA) in an adolescent population, potentially transforming the field of HIV prevention for young people. The study target population is sexually active, healthy male adolescents aged below 18 years. The study target is to enroll more than 50 participants with at least 50 participants receiving at least one injection. Participant recruitment will take approximately 12 months.

Study participation includes Step 1: a 5-week oral CAB 30mg QD safety lead-in followed by Step 2: a series of 5 intramuscular (IM) injections of 3 mL (600 mg) cabotegravir administered at 8-week intervals after a 4-week loading dose (injections at weeks 5, 9, 17, 25 & 33). Adherence support strategies (e.g., counseling, reminders, pill cases) will be included to support pill-taking during the first five weeks and to support retention during the injectable phase. A safety visit will follow each injection to ascertain pharmacokinetic-peak safety data, including injection site reactions. Step 3: A blood draw visit, the +8 Week Visit, will follow the week 33 injection to monitor CAB drug levels. All participants who have received at least one injection will be followed for 48 weeks after their last injection. Waning levels of cabotegravir (the PK tail) will be covered with locally sourced oral TENOFOVIR/EMTRICITABINE (TRADE NAME: TDF/FTC, TRUVADA®) for daily use for 48 weeks. In Step 3 participants may also choose to continue with 8-week dosing of injectable of CAB-LA for 48 weeks (5 additional injections beyond the initial 5 injections, administered at weeks +8, +16, 24, +32, +40, and +48.) Behavioral and acceptability data will be collected via computer-assisted self-interview (CASI). Total participant commitment for the entire study is up to 87 weeks, or approximately 1.5 years. We anticipate recruitment for the study will take approximately 12 months.

Participants who discontinue study product during Step 2 for any reason other than HIV infection or AE occurrence will be transitioned to open label TDF-FTC for 48 weeks.

There are in total three study sites:

- Adolescent and Young Adult Research at the Core Center (AYAR at CORE), Chicago, IL;
- St. Jude Children's Research Hospital CRS, Memphis, TN;
- Fenway Health CRS, Boston, MA.

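### The Step 3 schedules mark product at the Early Discontinuation visit (a CAB LA injection in Appendix IV, a TDF/FTC supply with no HIV test in Appendix III), and the protocol text and footnotes conflict with this

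*Protocol*

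**What the plan says.** Protocol Appendix IV is the Step 3 schedule for participants who continue CAB LA. It has six timed columns, +8 to +48 weeks, and a seventh headed "Early Discontinuation". The row "Injections (CAB LA" is marked in all seven. None of the seven footnotes restricts the last mark. Footnote 6 says that blood for plasma storage must be drawn before the injection.

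Appendix III is the schedule for participants on oral PrEP. Its row "Provision of Tenofovir/Emtricitabine", for three months' supply, is marked at +12, +24, +36 and Early Discontinuation. Footnote 3, attached to the HIV testing row, reads: "At least one HIV assay result must be available and reviewed the same day as sample collection and before product is administered".

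Section 5.16 covers participants who withdraw consent during a visit. In general that visit is "completed to the extent possible except for provision of study product and will be considered their final visit". Section 4.1 (Step 3) says that everyone who received an injection is followed for 48 weeks after the last one. Section 5.11.2 adds: "Participants with confirmed HIV infection during Step 3 will not receive oral Tenofovir/Emtricitabine", and says the same of CAB LA.

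SAP 2.1 describes the Step 3 injection option as "5 additional injections beyond the initial 5 injections, administered at weeks +8, +16, 24, +32, +40, and +48".

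**The concern.** Sites run visits from the schedule tables. Read literally, Appendix IV directs an injection of a depot that section 1.10 describes as impossible to remove or dialyse, at a visit after which no contact is planned. AE reporting ends with follow-up (section 6.1), so a reaction to that dose would be captured only through passive awareness under section 6.2. Appendix III directs three months of two antiretrovirals to a participant leaving the study, at a visit with no HIV test marked. Whether a participant is infected is what decides whether section 5.11.2 allows that supply at all. Both directions sit badly with rules elsewhere in the same protocol.

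**Working it through.** No sample size, power or event figure is involved. The check is a reading of cells, then a comparison with the text.

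**1. Are the cells read correctly?** The tables were extracted from PDF, so a shifted cell is possible. Each row checked has as many cells as column headers (six in Appendix III, seven in Appendix IV). The injection row has 7 marks for 7 columns, so no shift could move a mark into or out of Early Discontinuation. The Appendix III rows are only partly filled. A shift there is unlikely but cannot be fully excluded.

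**2. The Early Discontinuation columns side by side.**

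| Item | Appendix III | Appendix IV |
|---|---|---|
| Product | TDF/FTC, 3 months: marked | CAB LA injection: marked |
| HIV testing | blank | marked |
| Blood collection | blank | blank |
| Chemistry, liver function | marked | marked |
| History, medications, exam | blank | blank |
| Plasma storage | blank | blank |
| ISR evaluation | no such row | marked |
| HBsAb/HBcAb and HCVAb | marked | marked |

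**3. Is it an exit visit?** The protocol does not define Early Discontinuation for Step 3. Section 5.13 places repeat HCV antibody testing, and HBsAb/HBcAb testing where applicable, at the end of the study. In both appendices these tests are marked only at +48 and Early Discontinuation. The column is therefore built as a last visit.

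**4. Against section 5.16.** A participant who withdraws consent during a visit gets no study product at it. Appendix IV marks an injection in the column that such a visit would use.

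**5. Against section 4.1.** An injection given at the last visit becomes the last injection. The follow-up after it is then 0 weeks, against 48 planned.

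**6. Within Appendix IV.** Footnote 6 requires plasma-storage blood before injection, yet plasma storage and blood collection are blank in the column that marks the injection. HIV, chemistry and liver function tests are marked in that same column and need blood.

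**7. Within Appendix III.** TDF/FTC is marked at four visits: +12, +24, +36 and Early Discontinuation. HIV testing is marked at +12, +24, +36 and +48. So 3 of the 4 supply visits carry an HIV test, and the exception is Early Discontinuation.

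**8. SAP count, a separate matter.** The listed dates are +8, +16, +24 (printed without its sign), +32, +40 and +48. That is 48 / 8 = 6 injections, as in the timed columns of Appendix IV, against 5 stated. The total per full continuer is 5 + 6 = 11 by the dates and 5 + 5 = 10 by the stated count.

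**The case against.** The case on the other side has real content.

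- **Section 5.16 is narrow.** It opens with a qualifier and covers withdrawal of consent during a visit, not every last visit. This stands, so it would be too strong to say that the protocol bans product at all exit visits. If Early Discontinuation instead means stopping injections while staying in the study, an injection in that column contradicts its own label. Either reading needs reconciling.
- **Other controls exist.** Section 3.6 has the site contact the CMC about final evaluations when product stops early. Sections 5.11.2 and Appendix VI bar or hold product for HIV infection, HBV infection and toxicity, and a grid need not repeat them. This lowers the chance of a wrong dose but does not remove the contradiction.
- **The 48-week commitment is worded in two ways.** Sections 2.3 and 5.7 count from the last Step 2 injection, and Appendix IV also marks an injection at +48, the planned last visit. The follow-up limb therefore rests on the wording of section 4.1. The conflict with 5.16 does not depend on it.
- **The TDF/FTC supply may be tail cover.** Sections 4.1 and 4.2 provide it for 48 weeks after the last injection. It is listed among the study product regimens in 4.1 but is not a study agent for EAE reporting (6.2), so 5.16 may not reach it. The documents do not say that the exit supply is tail cover. The missing HIV test conflicts with footnote 3 either way. That footnote hangs on a row that is blank here and speaks of administering, but TDF/FTC is the only antiretroviral product in that schedule.
- **Section 5.8.1 mentions HIV testing with counselling at each visit.** That arguably covers the gap, but the schedule then disagrees with it.

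A reader might also infer more than the documents support. The median of 42.7 weeks to undetectable drug in men (section 1.5.2) was observed after the last of repeated injections in HPTN 077. It is not the persistence of one additional 600 mg dose. Nor would Step 3 results by number of doses be distorted, since neither document plans such an analysis. Finally, the missing HIV test is not common to both schedules, because Appendix IV marks one.

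**Conclusion.** The point holds as an internal contradiction that is wrong as written. It is firmest for the injection cell in Appendix IV, where the reading is certain and nothing in the footnotes limits it. The Appendix III point is a separate conflict with that schedule's own footnote and carries the small extraction doubt noted above.

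The possible harm is clinical and operational: unobserved exposure after exit, or product supplied without a current HIV result. SAP 6.4 records that enrolment stopped at nine, so only the few of these who reach Step 3 and attend an Early Discontinuation visit could be affected. People lost to follow-up or withdrawing between visits would not be. The primary safety analysis in SAP 8.1 ends 8 weeks after the last Step 2 injection or at Week 41, whichever is first, and is not affected. I take that window as governing, although Protocol 7.7.1 describes a longer one.

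The conclusion rests on treating Early Discontinuation as an exit visit, which the marked tests support but no text states. Low numbers limit the consequence. Because the matter concerns dosing of adolescents and is cheap to settle, it should still be corrected.

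**What to change.** 1. Define Early Discontinuation for Step 3. Reconcile that column in Appendices III and IV with sections 3.6, 4.1, 5.11.2 and 5.16 and with Appendix VI, so that the documents state one rule on whether product is provided at that visit. Which rule is for the sponsor to decide; none is proposed here.
2. If any product stays marked there, mark in the same column the HIV test and blood collection that the footnotes presuppose, including the pre-injection plasma sample under footnote 6 of Appendix IV. If the TDF/FTC supply is meant as tail cover, say so.
3. Separately, and as a minor correction, make the Step 3 injection count in SAP 2.1 agree with its six listed dates and with Appendix IV.

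The cost is an amendment to two schedule tables and one SAP sentence. No participants or visits are added. If Step 3 has already ended, the study report can state what was given at any Early Discontinuation visit.
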